Study Design:

The pilot study will be an interrupted time series cohort of 400 MSM. In two cities, a three-month baseline standard of care (SOC) period with measurement at 0 and 3 months will be followed by a 12-month intervention period with the measurement at 6, 9, 12, and 15 months. The longitudinal design will allow for 1) assessment of feasibility and acceptability outcomes, 2) development of the logistical and operational needs to provide the app-based intervention, and 3) development of estimates for key parameters to design a future, definitive study to determine intervention efficacy.

Standard of care will consist of the existing Blued app and local health services. Blued app access currently includes health education components such as information regarding HIV testing and pre-recorded health messages from Chinese celebrities. Participants will have access to in-person no-cost services for HIV testing and condom pick-up from local non-governmental organizations (NGOs) that support MSM in both cities.

At three months, participants will be provided with educational materials in the health portal as well as theory-based HIV prevention messages, along with home HIV test kits and condoms. This intervention will have a health portal that houses all HIV prevention functionalities. The exact nature of the interventions included will be further defined by the qualitative work, as additional services may be identified as essential to an HIV prevention package in China. These may include services such as peer support or stigma reduction. Additionally, participants will receive PrEP medication, laboratory, and care costs free of charge.

In the portal, users will be able to explore health-supporting functions of the app and access offline services, including behavioral risk assessments, an HIV prevention platform, HIV testing, linkage to care for those testing positive for HIV, in-app screening and referral to HIV pre-exposure prophylaxis (PrEP) and sexually transmitted infection (STI) services, and provision of PrEP with emtricitabine/tenofovir disoproxil fumarate (FTC/TDF).

Study Population:

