A total of 400 participants will be enrolled in the intervention with quarterly follow-up with a total of six surveys for each participant comprising enrollment/baseline (two surveys) and pilot intervention (four surveys). The survey will be team translated to ensure accuracy of the text and participant understanding.

Below is a diagram of the pilot study design:

[figure not shown]

Figure 1 Pilot Study Design Overview

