6.0 MEASURES

A summary table of study measures, and sources for each measure, are provided in the table below. Measurement of tenofovir-diphosphate (TFV-DP) levels will be conducted using liquid chromatography/tandem mass spectrometry methods on DBS samples. TFV-DP level can be translated to an interpretation that indicates mean number of days per week PrEP is ingested over a period of approximately one month. The cutpoint used will be TFV-DP levels considered a surrogate for substantial protection: >700 fmol/punch, a level indicating >4 doses/wk.

Construct	Measure	Data source	Definition	Analysis
PRIMARY OUTCOMES				
Feasibility	Home HIV test orders	Order fulfillment	Proportion of participants sent a home HIV test	Benchmark ≥ 30%
Feasibility	Condom orders	Order fulfillment	Proportion of participants sent 'choice' condom package	Benchmark ≥ 30%
Feasibility	PrEP initiation	Clinical site data	Proportion of participants receiving a PrEP prescription	Benchmark ≥ 20%
Acceptability	Systems Usability Scale ^{126, 127}	Survey	10-item scale, good score is >71	Benchmark: Good score (≥ 71 out of 100)
Acceptability	Ratings for intervention components ⁷²	Survey	Likert acceptability rating for each intervention component (e.g. home HIV test)	Benchmark: Acceptable ratings (≥ 3 out of 5)
PRELIMINARY EFFICACY ASSESSMENT				
HIV testing	HIV testing ^{44,128}	Survey	Change in median number HIV tests	GEE model
Condom use	Condom use ^{44,128}	Survey	Change in proportion of participants reporting always using condoms for anal sex	GEE model
PrEP Use	PrEP use ¹²³⁻¹²⁵	Laboratory data	Number participants with protective levels of TDF-DP	Descriptive report
THEORETICAL ASSESSMENT				
Prevention cascade	PrEP cascade levels ¹²⁹	Survey and clinical site data	PrEP awareness, willingness, prescription, persistence in care, and medication adherence	Descriptive and logistic regression
Theoretical assessment	Unified Theory of Acceptance and Use of Technology (UTAUT2) ¹²¹	Survey	Validated items for performance expectancy, effort expectancy, social influence, hedonic motivation, and habit.	Descriptive and GEE model to estimate SEM parameters
PROCESS OUTCOMES				
Process	New HIV testers	Survey	Proportion changing from never to ever HIV test	Descriptive report
Process	New condom users	Survey	Proportion changing from none to some condom use	Descriptive report
Process	Visits to local health clinics	Survey	Proportion receiving HIV services at health departments	Descriptive report

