10.3 Preliminary Efficacy Assessment

Preliminary efficacy assessments will describe differences in outcomes for the intervention, compared to the baseline period, for the median number of HIV tests and the proportion reporting all anal sex acts as condom-protected. A generalized estimating equations (GEE) repeated measures analysis will be conducted for the binary outcome of HIV testing (test/not testing). The GEE model will contain the seven time periods with primary comparisons of 0-month (first baseline) measurement to 6-month (end wash-out baseline period measurement and to 12-month (end first intervention period) measurement. Time will be considered as a fixed effect to compare proportion tested across intervals, with a random intercept for individuals. A similar GEE model will be conducted for the condom outcome (always/not always condom use). Logistic regression models will be fitted to understand PrEP cascade progressions, with the main analysis being any forward progress (yes/no) in the overall cascade between 0-month and 15-month measurements. These analyses will consider variables of progression in the PrEP cascade. Time at which cascade progress was made (e.g. 3 months) will be entered as a co-variate. A multifaceted approach to address missingness for our outcomes will be used. Primary analyses will treat values as missing at random. Sensitivity analyses will re-analyze data using both last-value-carried-forward and multiple imputation methods.

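### Section 10.3 counts seven periods for six surveys, labels month 6 as baseline although the intervention starts at month 3, and gives a GEE a random intercept

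*Combined protocol and SAP*

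**What the plan says.** Section 10.3 of the combined protocol and SAP sets out a GEE for whether a participant tested for HIV, and a similar model for always using condoms. Its main statements are:

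- Time factor: "The GEE model will contain the seven time periods".
- Primary comparisons: month 0 is set against "6-month (end wash-out baseline period measurement and to 12-month (end first intervention period) measurement".
- Dependence within a person: "Time will be considered as a fixed effect to compare proportion tested across intervals, with a random intercept for individuals".
- Missing data: "Primary analyses will treat values as missing at random", followed by "Sensitivity analyses will re-analyze data using both last-value-carried-forward and multiple imputation methods".

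Other sections describe the schedule and the outcome differently. The Schema (Study Design) has a three-month standard-of-care baseline whose "measurement at 0 and 3 months will be followed by a 12-month intervention period with the measurement at 6, 9, 12, and 15 months". Section 3.0 gives "a total of six surveys for each participant comprising enrollment/baseline (two surveys) and pilot intervention (four surveys"). Section 11.5 pays for six surveys and lists the same six months. The measures table in Section 6.0 defines the HIV testing outcome as "Change in median number HIV tests" and names a GEE as its analysis. Section 10.2 presents these analyses as comparisons of the intervention period with baseline, meant to inform the design of a later trial.

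**The concern.** The paragraph describes a different schedule from the one the trial will run, and it mixes two kinds of model. The labels matter most. A reader who takes month 6 as the end of baseline will report the 0 to 6 month change as background drift. Under the design, that change already contains exposure to the app, the home test kits and free PrEP. Aim 4 uses pilot estimates to design the efficacy study, so a mislabelled comparison could pass into its planning assumptions.

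The model sentence leaves two analysts free to fit different things: a GEE, which describes population proportions through a working correlation, or a random-intercept logistic model, whose coefficients are within-person. Section 10.4 adds the technology-acceptance constructs to the same models, so the ambiguity carries forward.

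**Working it through.** **1. Period count.** The plan's figure is 7. From Section 3.0, 2 baseline + 4 intervention = 6 surveys. From the Schema, quarterly measurement from month 0 to month 15 gives 15/3 + 1 = 6 time points, with 5 intervals between them. Neither count is 7. Section 10.3 itself takes month 15 as the last measurement for the PrEP cascade, so it offers no later visit to make up the number.

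**2. Labels against the design.** The intervention starts at month 3 and lasts 12 months, ending at 3 + 12 = 15.

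| Comparison | Section 10.3 label for the later month | Place in the Schema | Intervention time included |
|---|---|---|---|
| 0 to 6 | end of a wash-out baseline | first of four intervention measurements | 6 − 3 = 3 months |
| 0 to 12 | end of a first intervention period | third of four intervention measurements | 12 − 3 = 9 of 12 months |

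The Schema has no wash-out and only one intervention period, so both labels conflict with it. The first changes what the comparison means.

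**3. Effect of a seventh level.** An intercept plus six period indicators is 7 parameters. With six visits the design matrix has rank 6, so one effect is not estimable, and it is the one with no data. An exchangeable logistic GEE was fitted to simulated data (400 participants, six waves), declared first with six and then with seven levels. All six real coefficients and their robust standard errors agreed to four decimals. Months 0, 6 and 12 all have surveys, so both comparisons can be estimated.

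**4. GEE or random intercept.** The two candidates are:

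- GEE: logit P(Y = 1 at time t) = β_t, with a working correlation.
- Mixed model: logit P(Y = 1 at time t given b) = γ_t + b, with b normal with mean 0 and SD σ.

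On the proportion scale they can be made to agree: an assumed rise from 30% to 38% is 8 points from either, once the mixed model is standardised. As odds ratios they differ. The population-average value is (0.38/0.62)/(0.30/0.70) = 0.613/0.429 = 1.43. The within-person value is 1.53, 1.64, 1.78 or 1.95 for σ = 1, 1.5, 2 or 2.5.

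**5. Outcome.** Section 6.0 pairs a change in a median count with a GEE. Section 10.3 only describes the median and fits the GEE to tested or not tested. These are different outcomes.

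**6. Missing data.** Missing at random is an assumption, not a method, and an unweighted GEE is not in general valid under it. The illustration below assumes a constant true proportion of 30%, six waves and dropout that depends on the previous outcome, with 600,000 simulated participants per setting. The documents give no dropout rate. Entries are ranges of the month-12 estimate over random-intercept SDs of 1.5 and 2.5 and latent serial correlations of 0.6 and 0.8.

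| Dropout per wave (after a test, after none) | Retained at month 15 | Exchangeable GEE | Independence GEE |
|---|---|---|---|
| 1%, 3% | 89% | 29.9–30.0% | 30.4–30.8% |
| 2%, 8% | 73% | 29.5–29.9% | 31.2–32.6% |
| 5%, 10% | 64% | 29.7–30.0% | 30.9–32.1% |
| 5%, 15% | 53% | 29.0–29.8% | 31.9–34.6% |

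With exchangeable correlation the largest drift is 30.0 − 29.0 = 1.0 point, against a robust standard error of 2.5 to 3.4 points at 400 participants. From an assumed 17% the exchangeable range is 16.2–17.0%, a drift of at most 0.8 points.

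**The case against.** The best defence is that these are drafting slips in a secondary analysis. The pilot is not powered for change from baseline (Section 10.2), and none of the Section 10.1 benchmarks uses these models. An empty seventh level does no harm, the wording about comparing proportions points to a population-average analysis, and Section 6.0 is only a summary table. Most of this stands, and it rules out several stronger readings that a reader might infer:

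- **That the model cannot be fitted.** The six real effects are estimable. The count is wrong, but it does not block the analysis.
- **That the estimates will be seriously biased by dropout.** The larger figures in step 6 need an independence correlation, which the plan does not name. The largest also need heavy outcome-dependent dropout, which no document predicts. The completion bonus in Section 11.5 and the fall-off reports in Section 9.1 make lighter dropout plausible, though they do not ensure it.
- **That multiple imputation must become the primary analysis.** It is already planned as a sensitivity analysis and could reveal such drift. Moving it to remove at most about 1.0 point is a preference.
- **That the effect size is open to a large discrepancy.** The gap between 1.43 and 1.53–1.95 arises only if odds ratios are reported, and Section 10.3 does not call for them in these models.
- **That leaving months 3 and 15 out of the two primary comparisons is an error.** That is a design choice; both months remain in the time factor.

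The defence does not answer the month labels. They contradict the Schema and change what a named comparison measures.

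**Conclusion.** Section 10.3 is wrong as written on four points: the period count (seven against six), the month-6 and month-12 labels, the random intercept in a GEE, and the mismatch with Section 6.0 over which testing outcome is modelled. The label error has the most consequence, because it would present a change that includes three months of intervention as pre-intervention drift. The effect is limited to the preliminary efficacy results and the Section 10.4 models; the feasibility and acceptability conclusions are untouched.

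The textual conflicts need no assumption. The missing-data and odds-ratio figures are illustrations with assumed starting levels, dropout and correlation. They include nothing near the roughly 54% consistent condom use implied by the 46% inconsistent use in Section 1.0, so the 1.0-point limit is shown for the settings tested and not as a general bound.

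**What to change.** 1. State six time points: 0, 3, 6, 9, 12 and 15 months.
2. Classify months 0 and 3 as baseline and months 6, 9, 12 and 15 as intervention. Relabel both primary comparisons to match and remove the references to a wash-out and a first intervention period.
3. Replace the random intercept with a logistic GEE with exchangeable working correlation and robust standard errors, reporting proportions and differences per wave. Alternatively, name a random-intercept logistic model and report standardised proportions. Use the same choice for condom use and for Section 10.4.
4. Correct the Section 6.0 entry so that tested or not tested is the modelled outcome and the median number of tests is only described.
5. Keep multiple imputation as the planned sensitivity analysis.

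The cost is a few sentences of plan text and minor programming. No new data are needed and no participant procedure changes. The edits should be made before the analysis starts, so that the choice of model and labels does not follow the results.

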The study population will be self-reported HIV-negative Blued users who are 18 years of age or greater, were assigned a male sex at birth, report having anal sex with a man in the last 6 months, are able to complete a survey in standard Mandarin Chinese, are willing to provide two forms of contact information, are willing to update the Blued app with the Blued+ portal after the baseline period, are willing to complete quarterly surveys for the 15-month study period, and reside in metropolitan Beijing or Chengdu, China.

Study Size:

The sample for the pilot study will consist of approximately 400 MSM, 200 each in Beijing and Chengdu. All 400 men will be followed for 15 months.

Study Duration:

Recruitment activities will be conducted for three months or until 200 MSM have been recruited in each intervention city. After enrollment, MSM will have a follow-up period of 15 months for each participant.

Primary Objectives:

This study has four primary objectives:

1. Conduct a review of literature on behavioral and biomedical interventions offered in online and offline settings for MSM in China.
2. Develop a mathematical model of HIV transmission in Chinese MSM, informed by annual cross-sectional surveys, that accounts for behavioral, structural, and biological factors in order to estimate the impact of different scenarios of intervention provision and inform selection of intervention components for the pilot study.
3. Assess Blued+ intervention feasibility and acceptability in China, first by collecting qualitative data to inform the development of the Blued+ app components and service delivery and then by developing and pilot testing Blued+ among MSM in Beijing and Chengdu, China. This protocol includes only the pilot study portion of the overall study.
4. Use preliminary information from the pilot study to design a larger, definitive study of the efficacy of the prevention package for Chinese MSM.

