5.1.2 Informed Consent and Enrollment

Because men will not be consented and enrolled at an “in-person” visit, the consent process will be administered via the Blued app. Participants who are eligible based on screening and fraud checks will be provided an electronic study consent on a secure electronic survey platform and will be able to download and save a copy as well. Participants will be able to contact study staff should they have any questions during this process. The consent form describes all study procedures, including confidentiality and privacy, information about potential risks, discomforts, benefits of participation, and information regarding who they can contact with further questions. It also states that participation is voluntary, that participants may decide not to take part or to withdraw from the study at any time without penalty or loss of any benefit to which they might otherwise be entitled, and that study participation is in no way related to being able to access or continue getting care or services. Participants can refuse to answer any questions, and can withdraw from the study at any time.

A brief quiz will be developed to verify understanding of key elements of the consent form. After reviewing the consent form, potential participants will be forwarded to the consent quiz. Those who do not receive a sufficient score on the quiz will be directed back to the consent form for further review before completing the quiz.

Upon successful completion of the consent quiz, potential participants will provide consent using an electronic method to document signature on the electronic consent form. Informed consent must be obtained before any study procedures are performed. The consent form will be available in Mandarin Chinese.

Upon signing of the consent form, participants will notify participants to complete the baseline survey through Blued’s secure, encrypted survey platform.

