5.3 Intervention Description

During the intervention period, study participants will receive the enhanced version of the Blued app with Blued+ service. Blued+ serves as the primary participant-facing component of the intervention.

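### The main PrEP-cascade outcome runs from month 0 to month 15, so movement in the standard-of-care quarter, before participants receive Blued+, can be scored as progress

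*Combined protocol and SAP*

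**What the plan says.** **Outcome.** Section 10.3 fits logistic models to cascade movement, "with the main analysis being any forward progress (yes/no) in the overall cascade between 0-month and 15-month measurements". Section 6.0 lists the steps as "PrEP awareness, willingness, prescription, persistence in care, and medication adherence", with survey and clinical site data as the source.

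**Timing of the intervention.** The Schema (Study Design) describes "a three-month baseline standard of care (SOC) period with measurement at 0 and 3 months will be followed by a 12-month intervention period". It continues: "At three months, participants will be provided with educational materials in the health portal". Eligible men must be "willing to update the Blued app with the Blued+ portal after the baseline period" (Schema, Study Population). Section 5.3 agrees: "During the intervention period, study participants will receive the enhanced version of the Blued app with Blued+ service". Under Section 5.2, men in the baseline period have the existing app and local services.

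**Handling of time.** Section 10.3 also enters a covariate for when progress happened, in a sentence that opens "Time at which cascade progress was made (e.g. 3 months". Month 3 is the last measurement under standard of care.

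**Stated use.** Section 10.2 lists the cascade among the theoretical efficacy endpoints. It says the additional analyses will use the interrupted time series design and feed the design of a future trial.

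**The concern.** The outcome window opens one quarter before the intervention does. A single yes/no that spans the start of Blued+ cannot separate movement under standard of care from movement under the intervention. The plan's own example of a time of progress, month 3, confirms that progress recorded at the end of standard of care is meant to count.

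The early steps are the exposed ones. Awareness and willingness are survey answers. They can shift between months 0 and 3 through background trend, or because the month-0 survey prompted men to think about PrEP.

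For HIV testing and condom use, Section 10.3 at least sets out to compare the intervention with the baseline period. For the cascade it plans no such comparison. Two results are affected. The proportion progressing would be read as movement under Blued+ when part of it is not, and predictors of progress would mix two periods. Aim 4 uses pilot information to design the efficacy trial, so a mislabelled progression rate could carry into that planning.

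**Working it through.** **The plan's own figures.** The plan gives no figure for the cascade outcome. Its only precision figures (Section 10.2: ±4, ±5 and ±5 points at 20%, 30% and 50%) concern the binary benchmarks. With n = 400, exact (Clopper-Pearson) half-widths are 4.04, 4.60 and 5.01 points, which round to those values. The cascade window does not touch them.

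**Inputs from the documents.** Window 0 to 15 months (Section 10.3); Blued+ from month 3 (Schema, Section 5.3); surveys at 0, 3, 6, 9, 12 and 15 months (Section 11.5); 400 men (Section 3.2). Standard of care is thus one of five quarters, 3/15 = 20% of the window.

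**Assumed, because the documents give no rate.** A probability q of a forward step in each quarter, constant over time; no effect of Blued+; progress, once made, kept to month 15.

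**Formulas.** Counted as progressing over 0-15: 1 − (1 − q)^5. Over 3-15: 1 − (1 − q)^4. Share of 0-15 progressors whose first step fell in months 0-3: q / [1 − (1 − q)^5].

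| q per quarter | 0-15 (of 400) | 3-15 | First step in months 0-3 (of 400) | Share of 0-15 progressors |
|---|---|---|---|---|
| 2% | 9.6% (38) | 7.8% | 2% (8) | 0.208 |
| 5% | 22.6% (90) | 18.5% | 5% (20) | 0.221 |
| 10% | 41.0% (164) | 34.4% | 10% (40) | 0.244 |

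**If Blued+ works.** With 5% in standard of care and 15% in each intervention quarter, the counted proportion is 1 − 0.95 × 0.85^4 = 1 − 0.95 × 0.522 = 0.504. The share first moving in months 0-3 is 0.05/0.504, about 10%.

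**If the first quarter differs from the rest.** With 5%, 10% or 20% in months 0-3 and 2%, 5% or 10% in each later quarter, the share is s / [1 − (1 − s)(1 − q)^4], where s is the first-quarter probability. It runs from 13% (s = 5%, q = 10%) to 76% (s = 20%, q = 2%). The result depends heavily on rates that nobody yet has.

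**What moving the start to month 3 achieves.** In the table, the count falls by 1 − 7.8/9.6 = 19% at q = 2% and by 1 − 34.4/41.0 = 16% at q = 10%. The remaining 7.8% to 34.4% is background movement after month 3, which a later start cannot remove. A separate standard-of-care rate, set beside the intervention quarters, is needed to judge it.

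**Whether the timing covariate helps.** Time of progress exists only for men who progressed. In one simulated set of 400 men at q = 10%, all 158 with a recorded time had outcome yes, and the other 242 had no time. Coding the missing times as 0 gave perfect separation, and the logistic model did not converge. The covariate therefore cannot adjust for the standard-of-care quarter.

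**The case against.** The strongest reply is that little rests on this analysis. Section 10.3 says the models are there to understand progression. Section 6.0 lists the cascade as a theoretical assessment with no benchmark. Feasibility is judged on service uptake, including PrEP prescription, and protective drug levels are reported descriptively. Section 10.2 says the pilot is unpowered. All of this stands and limits the weight of the point.

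Three further arguments stand in part:

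- **Net change.** The wording can mean a comparison of two measurements. On that reading a man who becomes willing by month 3 counts only if he is still above his month-0 level at month 15. This narrows the problem but does not remove it.
- **Late steps.** Prescription, persistence and adherence are unlikely to move under standard of care, since study PrEP comes with the intervention and Section 1.0 says PrEP was not then approved in China. But any forward step counts, so the two early steps suffice.
- **Timing is recorded.** Movement before month 3 can be identified from planned data. That makes the repair feasible; it does not make it part of the plan.

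A reader might also infer that consent drives an early shift, since "The consent form describes all study procedures". Section 5.1.2 does not support this: consent and its quiz come before the baseline survey, so their immediate effect should largely be in the month-0 level already. Nor do the documents show that Blued+ does not exist before month 3. Section 5.3.2 speaks only of additional components unlocking then. What the Schema and Section 5.3 support is that participants receive the portal after the baseline period.

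**Conclusion.** The point holds as a mismatch between outcome window and design. As written, the main cascade outcome scores movement from the standard-of-care quarter as progress, at least where it persists to month 15. No contrast between baseline and intervention is planned for the cascade, and the timing covariate does not supply one.

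The size is unknown. The 21% to 24% share rests on a constant 2% to 10% per quarter, no Blued+ effect and no loss of progress. It falls to about 10% at 5% in standard of care and 15% per intervention quarter. A reader might take about a quarter of the progressors to be spurious; the documents give no rate that would support that as an estimate. A reader might also expect a month-3 start alone to isolate the effect of Blued+; it would not, because later background movement stays in.

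The primary benchmarks are unaffected. The change should be made because the result informs the later trial and the repair is cheap.

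**What to change.** In Section 10.3:

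1. Define the main cascade outcome as forward progress from the man's month-3 level, the last measurement before the intervention, to month 15. State whether this is net change at month 15 or any step reached on the way.
2. Report progress from month 0 to month 3 separately as the standard-of-care rate, beside each intervention quarter (3-6, 6-9, 9-12, 12-15), so that windows of equal length are compared.
3. In each quarter, take as denominator the men not yet at the top step at its start, and show results by starting step, because men higher up have less room to move.

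**Cost.** A few sentences and a recoded outcome; every survey needed is already scheduled. The reported proportion progressing becomes smaller. Men who miss the month-3 survey fall under the stated missing-data plan. Under its last-value-carried-forward sensitivity analysis, such a man takes his month-0 level, which puts the standard-of-care quarter back into his window; the report should say so. Section 10.3 needs editing in any case, since its seven time periods and 6-month wash-out do not fit six surveys and a month-3 start.

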10.4 Theoretical Assessments

Theoretical assessments will include descriptive and regression models to explore PrEP cascade level and constructs of the UTAUT2. We will add UTAUT2 constructs as independent variables to the above specified GEE models. Analyzing constructs of the UTAUT2 model will allow for estimation of structural equation modeling coefficients to inform assessment of required sample size to determine theoretical components of an eventual SEM in a future RCT of the intervention (Aim 4). Analysis will also inform our understanding of whether the theoretical model is appropriate for capturing pathways of the intervention effects. Process outcomes will be reported with descriptive statistics.

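### The main PrEP-cascade outcome and the new-condom-user count record only favourable moves, so both exceed zero without any net change; report backward moves and a standard-of-care reference beside them

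*Combined protocol and SAP*

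**What the plan says.** The design is a single cohort: "The pilot study will be an interrupted time series cohort of 400 MSM". It has a within-person comparison period, since "a three-month baseline standard of care (SOC) period with measurement at 0 and 3 months will be followed by a 12-month intervention period".

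Three outcomes are defined in the favourable direction:

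- **PrEP cascade.** The levels in 6.0 are "PrEP awareness, willingness, prescription, persistence in care, and medication adherence", taken from survey and clinical-site data. Section 10.3 fits logistic models to study progression, "with the main analysis being any forward progress (yes/no) in the overall cascade between 0-month and 15-month measurements". The time at which progress occurred enters as a covariate.
- **New condom users** (6.0, process outcome): "Proportion changing from none to some condom use".
- **New HIV testers** (6.0, process outcome): "Proportion changing from never to ever HIV test".

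For none of the three does the plan give a backward count, a net change, an at-risk denominator or a standard-of-care rate.

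Other planned analyses bear on the point. Section 10.4 states "Theoretical assessments will include descriptive and regression models to explore PrEP cascade level and constructs of the UTAUT2" and "Process outcomes will be reported with descriptive statistics". Section 10.3 plans GEE models for HIV testing (tested or not) and for condom use (always or not always). Section 10.2 says that the efficacy, cascade and process assessments will draw on the interrupted time series design and inform a future trial. Section 10.1 rests the primary conclusion on separate feasibility and acceptability benchmarks.

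**The concern.** Willingness, persistence in care, adherence and condom use can all go down as well as up. A count of upward moves alone is positive whenever people fluctuate or answer a survey inconsistently, even if as many men go backward. A randomised control arm would show that background level. Here there is none, and the one internal reference, the 0 to 3 month interval, is not used for these outcomes. For the cascade it is absorbed into the 0 to 15 month window, so progress made before Blued+ opens at month 3 counts as well.

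What is at stake is the hand-over to Aim 4. If a one-way proportion is taken as a preliminary effect when the larger trial is designed, background movement is carried along as if it were intervention effect.

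**Working it through.** **Plan's own figures.** The plan states no figure for these outcomes. Its only precision figures (10.2) are 95% half-widths of 4, 5 and 5 points at 20%, 30% and 50%. Exact intervals at n = 400 give 4.04, 4.60 and 5.01, so these are reproduced. The point does not depend on them.

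**Inputs.** From the documents: n = 400; surveys at 0, 3, 6, 9, 12 and 15 months (five quarterly intervals, four of them under intervention); five cascade components. All transition, reliability and hazard rates below are assumptions, because the documents give none. Steps 1 to 4 hold the population distribution constant, so true net change is zero.

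**1. One survey item, unreliability only.** Share moving up = (1 − κ) × p × (1 − p). For willingness with p = 0.5 at both surveys:

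- κ = 0.8: 0.2 × 0.25 = 5% (20 men)
- κ = 0.6: 0.4 × 0.25 = 10% (40 men)
- κ = 0.4: 0.6 × 0.25 = 15% (60 men)

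The same share moves down.

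**2. Six-level cascade (no level reached, plus five components).** Each man attempts a one-level move with probability 0.1 to 0.4 per quarter, with acceptance set so that the distribution stays fixed. Two distributions were used: equal sixths, and a bottom-heavy one (30, 40, 15, 8, 5 and 2%).

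| Distribution | Attempt rate | Up, 0–15 months | Down | Net | Up, 0–3 months |
|---|---|---|---|---|---|
| Bottom-heavy | 0.1 | 12.3% (49 men) | 12.3% | 0 | 3.0% |
| Bottom-heavy | 0.4 | 28.2% (113 men) | 28.2% | 0 | 12.0% |
| Equal | 0.1 | 15.8% (63 men) | 15.8% | 0 | 4.2% |
| Equal | 0.4 | 31.9% (127 men) | 31.9% | 0 | 16.7% |

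These compare month 15 with month 0. If forward progress means being above the month-0 level at any survey, the range is 13.4% to 44.7%. If it means any upward step between consecutive surveys, it is 14.3% to 60.4%. The wording of 10.3 does not settle which is meant.

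**3. What each summary would show.** A one-sample 95% interval for the forward share is 12.3% ± 1.96 × √(0.123 × 0.877/400) = ± 3.2 points, well clear of zero. The paired interval for net change is 0 ± 1.96 × √((0.123 + 0.123)/400) = ± 4.9 points. At 31.9% the two half-widths are 4.6 and 7.8 points.

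**4. New condom users.** For a stationary two-state process, share moving none to some over k quarters = π(none) × π(some) × (1 − λ^k), where λ = 1 − exit rate − return rate. With 20% in none, quarterly exit 0.1, 0.2 or 0.3 (return 0.025, 0.05 or 0.075) and k = 4:

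- 0.16 × (1 − 0.875⁴) = 6.6% (26 men)
- 0.16 × (1 − 0.75⁴) = 10.9% (44 men)
- 0.16 × (1 − 0.625⁴) = 13.6% (54 men)

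Equal numbers stop. As a share of the none group this is 33% to 68%, so the unstated denominator matters. Other splits and mobility over five quarters run from 0.16 × (1 − 0.9375⁵) = 4.4% to 0.25 × (1 − 0.6⁵) = 23.1%. With no true change and random misreporting e at each survey, the share is e(1 − e): 4.75% at e = 0.05 and 9.0% at e = 0.10 (19 and 36 men).

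**5. New HIV testers (a different mechanism).** With a constant annual first-test probability a among never-testers and no intervention effect, the share by month 15 is 1 − (1 − a)^(15/12).

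| a | By month 3 | By month 15 |
|---|---|---|
| 10% | 2.6% | 12.3% |
| 20% | 5.4% | 24.3% |
| 38% | 11.3% | 45.0% |
| 52% | 16.8% | 60.0% |

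The last two values of a borrow the annual testing prevalences in section 1.0. Those describe MSM generally, not never-testers, and serve only to span a range.

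**The case against.** The strongest reply is that nobody proposes to judge the intervention on these figures. The process outcomes are descriptive, the cascade model asks who progresses, and 10.2 says that the pilot is not powered for change from baseline. That stands, and it limits the point to reporting and to use in later design.

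A reader might go further and infer that the plan would declare success whatever happened. The documents do not support this: none of the three outcomes has a threshold, and none enters the decision in 10.1. Nor is it right that the rule can never return no change. Each man is coded yes or no, and if months 0 and 15 are compared, someone who rises and falls back is a no.

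A reader might also group new HIV testers with the other two. That fails as well: ever having tested cannot truly reverse, so no backward move is being ignored.

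Other analyses help in part. Descriptive cascade levels could reveal a lack of net change, although no net estimate or transition table is specified. The condom GEE moves both ways, but a man who goes from some use to none stays within not always, so that model cannot see him. The timing covariate shows that the data can separate the periods, but a covariate is not a standard-of-care rate.

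Finally, the magnitudes are assumed. Survey unreliability does not describe a prescription taken from clinic records. Study PrEP starts only after month 3, so few men may hold upper cascade levels to lose at month 0. This too stands.

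**Conclusion.** The concern holds in a limited form. The main cascade outcome and the new-condom-user count are one-directional measures of states that can reverse, in one cohort without a parallel control or a planned reference rate. They will be above zero with no net change and cannot alone be read as benefit or carried into the next trial's design. That direction needs only some two-way movement or response error. The sizes shown (about 12% to 32% for a six-level cascade, 4% to 23% for none-to-some condom use) depend wholly on assumed rates and are not forecasts. For new HIV testers the issue is smaller: background accrual without an at-risk denominator or comparison rate. The pilot's primary feasibility and acceptability conclusions are unaffected. This is a cheap and worthwhile improvement, not a flaw in the main analysis.

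**What to change.** In 6.0 and 10.3:

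1. Keep the logistic progression model, labelled exploratory. State whether forward progress compares month 15 with month 0 or counts any rise in between, and how a man who rises and falls back is coded.
2. Beside it, report two-way transition tables for cascade level and for none/some condom use: per cent up, per cent down, and the net difference with a paired 95% CI.
3. Show the 0–3 month standard-of-care interval separately from the 3–15 month intervention interval.
4. For new HIV testers, use baseline never-testers as the denominator and set the rate in the standard-of-care quarter beside the rates in the intervention quarters.
5. State that net change in one cohort cancels symmetric fluctuation only; it does not remove secular trend or dropout bias.

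Replacing the progression model with an ordinal model of end level is a matter of preference and is not needed.

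The cost is SAP wording and one extra table from the six planned surveys and clinic data. The downside is less favourable headline figures.
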